# **Revision History**

Version	Date	Author(s) and Role	Summary of Changes/Comments
0.1	17-07-2019	Trial statistician	Information from protocol included
0.2	19-07-2019	Trial statistician	Changes made for senior statistician's comments on v 0.1
0.3	12-08-2019	Trial statistician	Changes made for chief investigator's comments on v 0.2
1.0	10-09-2019	Trial statistician	Final version

#### LIST OF ABBREVIATIONS

AE	Adverse event
AR	Adverse reaction
BMI	Body Mass Index
BP	Blood pressure
CHD	Coronary heart disease
CV	Cardiovascular
CVD	Cardiovascular disease
EQ-5D	EuroQol five dimensions
HADS	Hospital Anxiety and Depression Scale
MI	Myocardial Infarction
MVPA	Moderate to Vigorous Physical Activity
PA	Physical Activity
RCT	Randomised Controlled Trial
REC	Research Ethics Committee
RPAQ	Recent Physical Activity Questionnaire
SAE	Serious Adverse Event
SAR	Serious Adverse Reaction
SOP	Standard Operating Procedure
SUSAR	Suspected Unexpected Serious Adverse Reactions
UHL	University Hospitals of Leicester

# **1** Introduction

This Statistical Analysis Plan (SAP) outlines the proposed statistical analyses for the MAP study, where a detailed and comprehensive description of the statistical methods is provided. The MAP Study is a randomised controlled trial that is being conducted to assess the effectiveness of a low-cost pragmatic intervention to increase daily physical activity at 12 months in participants with multimorbidity.

The structure and content of this SAP provides sufficient detail to meet the requirements identified by the International Conference on Harmonization of Technical Requirements for Registration of Pharmaceuticals for Human Use (ICH): Guidance on Statistical Principles in Clinical Trials . All work planned and reported for this SAP will follow nationally and internationally accepted guidelines, published by the American Statistical Association and the Royal Statistical Society for statistical practice .

The purpose of this SAP is to outline the planned analyses that are to be performed on the data to support the completion of the study publication for protocol V6 20\_06\_18. The SAP will be amended if substantial changes are made to the planned analyses, and in any case, will be finalized before the database lock for this study. Exploratory post-hoc or unplanned analyses not necessarily identified in this SAP may be performed on these data as required. These analyses will be clearly identified in the study publication.

The reader of this SAP is encouraged also to read the clinical protocol for details on the conduct of this study, and the operational aspects of clinical assessments and timing for the process of completing a patient in this study.

The outlined boxes in this SAP represent information from the protocol. The analyses will be carried out by the Trial Statistician ([name]) and supervised by the Senior Statistician ([name]) to ensure the integrity of the data processing at all stages.

# **1.1 Study Objectives**

### **1.1.1** Primary objective

To assess the effectiveness of a low-cost pragmatic intervention to increase daily physical activity at 12 months in participants with multimorbidity

### **1.1.2** Secondary objectives

- To assess the effectiveness of a structured self-management education programme on improving health-related behaviours such as adherence to medication or treatment regimes, communication and physical wellbeing;
- To assess the effectiveness of the structured education programme on improving self-reported quality of life;
- To assess accessibility and effectiveness of implementing the programme in a population with multimorbidity.
- To assess whether the intervention affects development of existing long term conditions or incidence of new long term conditions in the 5 years following the study

# 1.2 Study design

### 1.2.1 Summary

The study is a randomised controlled trial (RCT) which will test the effectiveness of a tailored structured self-management education programme with text message support on the primary (overall volume of physical activity) and secondary outcomes compared with usual care.

Participants with two or more chronic conditions will be recruited from primary and secondary care and randomised to attend the self-management structured education programme or continue receiving usual care.

### 1.2.2 Randomisation

Participants will be randomised 1:1; stratified by gender (male; female) and ethnicity (White European; other) to either intervention or control groups.

If two people are taking part from the same household they will be randomised to the same arm to prevent contamination taking place.

Both control and intervention participants will be informed of the outcome of the randomisation. In addition intervention participants will be sent a letter confirming the date and the venue of the education sessions.

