### **1.2.6** Sample size calculations

The primary outcome is change from baseline to 12 months average daily physical activity, as quantified by the Euclidean norm minus one (ENMO) method measured in milligravity units (mg). This is the main measure of activity derived from the activity monitor. In order to detect a minimum clinically significant difference of 2.1 mg, which is equivalent to an overall increase in physical activity volume of approximately 30 minutes of light walking at 4km/h, assuming a standard deviation of 5.3 mg [1], a power of 80% and significance level of 5%, the sample size requires 202 participants. To allow for 20% loss to follow-up and 20% non-compliance of the activity monitor, we will therefore need to recruit 338 participants (169 in each group).

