# 3.4 Per-protocol Population

The per protocol (PP) population are those who were compliant with the protocol and have complete data for the analysis concerned on 'by analysis' basis. In the control arm, the PP population will include all participants randomised to that arm with complete outcome data. In the intervention arm, the PP population will be defined as participants who have attended at least one group session of the programme and have outcome with complete data. This will be a sensitivity analysis.

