# **4** General Issues for Statistical Analysis

### 4.1 Multiplicity, Multiple Comparisons and Interim Analyses

All tests and reported p-values will be two-sided, where a p-value of < 0.05 will be considered to be statistically significant. Estimates will be presented with 95% confidence intervals. There will be no formal adjustment for multiple significance testing. The outcomes however, are clearly categorised by the degree of importance (primary and secondary). No formal interim analyses were planned.

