# 4.5 Primary Endpoint Analysis

### 4.5.1 Primary Analysis of Primary Endpoints

The primary outcome is change in overall volume of physical activity (average acceleration, ENMO) from baseline to 12 months. For the primary outcome treatment arm will be compared using linear regression modelling with

1. a binary indicator for randomisation group as the explanatory variable

2. terms for stratification factors (gender and ethnicity) as confounders

3. adjustment for the change from baseline in accelerometer wear time and baseline overall volume of physical activity.

The primary analysis at 12 months will be based on complete data.

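### Household pairs share an arm by design, but the primary model treats every participant as independent, so its 5% test is mildly anti-conservative if correlated pairs are enrolled

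*SAP*

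**What the plan says.** The basic allocation is individual: "Participants will be randomised 1:1; stratified by gender (male; female) and ethnicity (White European; other) to either intervention or control groups." Section 1.2.2 then adds the exception: "If two people are taking part from the same household they will be randomised to the same arm to prevent contamination taking place."

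Section 4.5.1 specifies the confirmatory analysis: "For the primary outcome treatment arm will be compared using linear regression modelling with" terms for arm, gender and ethnicity, plus "adjustment for the change from baseline in accelerometer wear time and baseline overall volume of physical activity." It names no household random effect, clustered variance or generalised estimating equation.

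The per-protocol, imputation, sessions-attended, interaction and subgroup analyses (4.5.2 and 4.7) use the primary model or its principles, and section 4.6 treats the secondary outcomes in a similar way. Section 4.6 does promise to check assumptions and consider other parameterisations, but it concerns secondary endpoints and does not mention clustering.

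The significance rule is in section 4.1: "All tests and reported p-values will be two-sided, where a p-value of < 0.05 will be considered to be statistically significant." The sample size in section 1.2.6 includes no allowance for households.

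**The concern.** When two people can only be allocated together, they form a cluster of size two. Ordinary regression standard errors assume that residuals are independent between participants. If the residuals of co-resident participants are positively correlated, each same-arm pair carries less information about the arm effect than two unrelated people do, and the ordinary standard error is too small.

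The SAP's own reason for the rule, contamination, presumes that people in one household influence each other's behaviour. That makes a positive correlation in activity plausible. Adjusting for baseline activity and gender may reduce it, but does not remove change that the two share over the 12 months.

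At stake is the single confirmatory test. A result close to 0.05 could fall on either side depending on whether households are recognised, and a choice made after seeing the result would be open to criticism.

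**Working it through.** **Inputs from the SAP.** Section 1.2.6: "In order to detect a minimum clinically significant difference of 2.1 mg", and "assuming a standard deviation of 5.3 mg [1], a power of 80% and significance level of 5%, the sample size requires 202 participants." Two-sided 5% level (section 4.1). Allowances of 20% for loss to follow-up and 20% for monitor non-compliance; 338 recruited, 169 per group.

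**Inputs not in the SAP (assumed).** f is the share of analysed participants whose household partner is also analysed, taken as 5 to 20%. rho is the within-household correlation of the covariate-adjusted outcome, taken as 0.1 to 0.5.

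**Step 1: reproduce the plan's figures.** The normal approximation gives 2 × (1.960 + 0.842)² × 5.3² / 2.1² = 100 per arm. The exact t calculation needs 101 per arm, or 202 in total (power 80.02%). Recruitment: 202 / (1 − 0.40) = 336.7, or 168.3 per arm, which rounds up to 169 and gives 338. Both figures follow under independence, so no design effect was built in.

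**Step 2: design effect.** Among n participants in an arm, n × f / 2 are complete pairs. The variance of the arm total is nσ² + 2 × (nf/2) × rho × σ² = nσ²(1 + f × rho). Hence DE = 1 + f × rho.

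**Step 3: consequences.**
- Shortfall in the model standard error = 1 − 1/√DE.
- True type I error = 2 × (1 − Φ(1.96/√DE)).
- Power of a correctly sized test: non-central t on 200 degrees of freedom, with non-centrality 2.1 / (5.3 × √(2/101) × √DE) = 2.816/√DE.

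| f | rho | DE | Model SE too small by | True type I error | Power, correctly sized test |
|---|---|---|---|---|---|
| 5% | 0.1 | 1.005 | 0.2% | 5.1% | 79.8% |
| 5% | 0.3 | 1.015 | 0.7% | 5.2% | 79.4% |
| 10% | 0.3 | 1.03 | 1.5% | 5.3% | 78.8% |
| 20% | 0.3 | 1.06 | 2.9% | 5.7% | 77.7% |
| 20% | 0.5 | 1.10 | 4.7% | 6.2% | 76.2% |

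With f = 0 or rho = 0 the type I error stays at 5.0%.

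**Step 4: check by simulation.** An unadjusted two-sample t test with 202 participants, 40,000 runs per setting, rejected in 5.2% (f 5%, rho 0.3), 5.4% (10%, 0.3), 5.8% (20%, 0.3) and 6.2% (20%, 0.5) of runs. This agrees with the formula.

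**Step 5: power of the test as planned.** The last column describes the corrected test. At DE = 1.10 the uncorrected test has power of about 1 − Φ((1.972 − 2.816)/√1.10) = 79%, but at a true level of 6.2%.

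**The case against.** The strongest reply is that the consequence is conditional and probably small. The household rule begins with an if. Each member must separately have two or more chronic conditions, be aged 40 to 85, walk independently and not be frail, so pairs may be rare. A pair matters only if both members are analysed. With the 40% planned allowance and losses independent within households (an assumption), 10 to 30% of recruits in pairs becomes 0.6 × 10% to 0.6 × 30%, or 6 to 18%, of those analysed. All of this stands. It limits the size of the problem but does not supply the missing household term.

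A reader might infer more than the SAP supports in three ways:

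- **That every interval in the trial is too narrow.** This does not follow. In sex-specific analyses the members of a mixed-sex pair fall in different strata, so the effect can be absent. For the arm-by-sex interaction, positive correlation within mixed-sex pairs can make the ordinary standard error too large.
- **That group delivery is part of the same error.** Section 3.4 refers to participants who have "attended at least one group session of the programme", so sessions are held in groups. But the SAP gives no group size, no intraclass correlation and no statement that people stay in one group. Any inflation figure would rest wholly on assumed values.
- **That the trial is underpowered and must be enlarged.** Over the assumed range, power falls by at most about four percentage points.

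**Conclusion.** The omission is real: section 1.2.2 allocates household members together, section 4.5.1 ignores this, and nothing else in the SAP repairs it. For the overall arm effect the standard error is too small whenever pairs are analysed and their adjusted outcomes are positively correlated. For f of 5 to 20% and rho of 0.1 to 0.5, the excess over the nominal 5% is about 0.1 to 1.2 percentage points.

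It would be too strong to state as fact that the type I error exceeds 5%, because the SAP gives neither f nor rho and the error disappears if either is zero. The likely effect is modest. It still deserves correction because it bears on the one confirmatory test, its true size cannot be known from the plan, and the remedy is almost free.

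**What to change.** In section 4.5.1, state that standard errors will be clustered (robust) by household, with participants who have no enrolled household partner as clusters of one. Carry this into the per-protocol, sessions-attended, interaction, subgroup and secondary models, and into the estimation step after multiple imputation. Clustered variance also handles the sex-specific and interaction analyses, where the error may be absent or reversed. Report the number of household pairs randomised and the number with both members analysed. Make the change before database lock.

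The cost is some SAP wording and one option in the regression command; the household link was already needed to apply the allocation rule. Clusters would be plentiful: with f = 20% of 202 there would be about 20 pairs and 162 singletons, or 182 clusters. Over the assumed range, intervals widen by up to about 4.9% (√1.10 = 1.049), and the power at 202 analysed is about 80% down to 76%. If no pairs are enrolled, the result is an ordinary robust standard error. The sample size need not be recalculated. An analysis clustering by education group could be added as an optional sensitivity analysis.

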### **1.2.3 Study treatment interventions**

This will be a randomised control trial with an intervention group and a control group.

1) Intervention group: Those randomised to the intervention group will be invited to attend four patient-centred education sessions of the structured education programme and to receive regular reminders with Short Message Service (SMS) messages (text messages) after the first session. The programme focuses on promotion of personalised physical activity and health-related self-management activities, which impact on quality of life.

These structured education sessions have been developed during an iterative process in conjunction with PPI work and other stakeholders through the use of existing infrastructure consisting of Diabetes Education and Self-Management in on-going and Newly Diagnosed (DESMOND) groups and a network of trained facilitators.

2) Control group: No change in the usual care of these participants will take place and they will continue with their routine care management in line with their direct care team's current recommendations for people with multimorbidity.

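### The SAP treats all participants as independent although the programme is delivered in groups and households share an arm, so the stated 80% power and 5% error are not assured

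*SAP*

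**What the plan says.** **Delivery.** SAP section 1.2.3 states that the intervention arm is "invited to attend four patient-centred education sessions of the structured education programme". That sentence alone does not say that people attend together. Section 3.4 does: the per-protocol population in the intervention arm must have "attended at least one group session of the programme". Section 4.5.2.1 repeats that these are group sessions. Controls continue with usual care.

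**Allocation.** Under section 1.2.2, two people from one household go to the same arm. The same section says that "intervention participants will be sent a letter confirming the date and the venue of the education sessions".

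**Sample size.** Section 1.2.6 uses a "minimum clinically significant difference of 2.1 mg", "assuming a standard deviation of 5.3 mg", and concludes that with "a power of 80% and significance level of 5%, the sample size requires 202 participants". It mentions no group size, ICC or design effect.

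**Analysis.** In section 4.5.1, "treatment arm will be compared using linear regression modelling with" terms for arm, gender, ethnicity, change in wear time and baseline activity. There is no term or robust variance for education group or household. Section 4.6 carries the same approach to the secondary outcomes. The analyses in 4.5.2.1 to 4.5.2.4 cover the per-protocol set, imputation, number of sessions attended and interactions, and none of them covers clustering.

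**The concern.** People who attend sessions together share facilitators, venue and peers, so their outcomes may be correlated. Controls have no such grouping. This is a partially nested design, with possible correlation by education group in one arm only. The household rule adds a second, smaller source of dependence in both arms.

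Ordinary regression assumes independent errors. If education groups differ, the variance of the intervention mean is larger than the model reports, and the confidence interval for the primary comparison is too narrow. Section 4.1 rests the trial's conclusions on a two-sided p below 0.05 and on 95% intervals, so the headline inference is affected. The error structure of the primary model belongs in an analysis plan, and section 4.5.1 fixes it.

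**Working it through.** **Inputs from the SAP.** Difference 2.1 mg, SD 5.3 mg, 80% power, 5% level (1.2.6); two-sided (4.1); 1:1 allocation (1.2.2); 202 evaluable and 338 recruited (1.2.6).

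**Assumptions, not in the SAP.** Analysed group size m of 6, 8 or 10; ICC of 0.01, 0.05 or 0.10; every analysed intervention participant belongs to one group.

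**Step 1: reproduce the plan.** An exact two-sample t-test needs 101 per arm, which is 202 in total, with power 80.0%. The normal approximation used below gives 80.4% at 101 per arm. For recruitment, 202 / (1 - 0.40) = 336.7, which rounds up to 169 per arm, or 338. Both figures reproduce under independence, so they contain no hidden allowance for clustering.

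**Step 2: formulas.** The design effect, in the intervention arm only, is D = 1 + (m - 1) × ICC.

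- True standard error = 5.3 × √((1 + D) / 101). The planned model assumes 5.3 × √(2 / 101) = 0.746.
- Error of the planned test = 2 × [1 - Φ(1.96 × √(2 / (1 + D)))].
- Power of an analysis that allows for clustering = Φ(2.1 / true SE - 1.96).
- Evaluable total for 80% power = 101 × (1 + D), rounded up to equal arms.

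**Step 3: one case in full (m = 8, ICC 0.05).** D = 1 + 7 × 0.05 = 1.35. True SE = 5.3 × √(2.35 / 101) = 0.808, which is 1.084 times the assumed value. Error = 2 × [1 - Φ(1.96 / 1.084)] = 7.1%. Power = Φ(2.1 / 0.808 - 1.96) = 73.8%. Evaluable total = 101 × 2.35 = 237.4, so 238.

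**Step 4: the range.**

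| m | ICC | D | Error, planned test | Power, clustering allowed for | Evaluable total for 80% |
|---|---|---|---|---|---|
| 6 | 0.01 | 1.05 | 5.3% | 79.4% | 208 |
| 8 | 0.01 | 1.07 | 5.4% | 79.0% | 210 |
| 10 | 0.01 | 1.09 | 5.5% | 78.7% | 212 |
| 6 | 0.05 | 1.25 | 6.5% | 75.6% | 228 |
| 8 | 0.05 | 1.35 | 7.1% | 73.8% | 238 |
| 10 | 0.05 | 1.45 | 7.7% | 72.0% | 248 |
| 6 | 0.10 | 1.50 | 8.0% | 71.2% | 254 |
| 8 | 0.10 | 1.70 | 9.2% | 67.8% | 274 |
| 10 | 0.10 | 1.90 | 10.4% | 64.7% | 294 |

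The two percentage columns belong to different tests. The error is that of the planned, unadjusted test when groups differ but the mean effect is zero. The power is that of an analysis that allows for clustering.

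**Step 5: simulation of the unadjusted t-test** (20,000 runs per setting). With m = 8, the error was 5.6%, 7.0% and 9.0% at ICC 0.01, 0.05 and 0.10, in line with the formula. At a true difference of 2.1 mg, the unadjusted test still rejected in 76-80% of runs across these settings, because its standard error is too small.

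The household effect cannot be sized, because the SAP does not say how many households contribute two people.

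**The case against.** **The ICC may be negligible.** The SAP gives no ICC or group size. At ICC 0.01 the power loss is about one point and the error is 5.3-5.5%. This stands: the size of the problem is unknown, and a reader should not infer that the 80% and 5% figures definitely fail.

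**The error inflation is conditional.** If the programme changes nobody and group members do not influence each other, education groups induce no correlation, and the 5% level holds apart from the household rule. This stands. Intervals are still too narrow whenever groups differ, whatever the mean effect.

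**No single test has both faults in full.** A reader might combine an error near 10% with power near 65%. That would be wrong, for the reason given with the table: the planned test keeps most of its nominal power by overstating its precision.

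**There may be margin in the power.** If 5.3 mg is the SD of change and the baseline to 12-month correlation is 0.7 (assumed), adjusting for baseline multiplies the variance by (1 + 0.7) / 2 = 0.85. In the middle case clustering multiplies it by (1 + 1.35) / 2 = 1.175, and the two nearly cancel (0.85 × 1.175 = 1.00). Also, if the second 20% loss applies only to those who remain, 338 × 0.64 = 216 are evaluable, which gives about 82-83% power under independence. Both margins are possible and neither is guaranteed. They concern power only and do not correct the standard error.

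**Delivery details are unknown.** The SAP does not say whether the same people stay together for all four sessions. Section 4.5.2.3 allows for people who attend none, and they would dilute the clustering. The letter in 1.2.2 confirms a date and a venue; that it identifies a fixed group is an inference. These points bear on the choice of model and the size of the effect, but do not justify leaving clustering out.

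**Conclusion.** The point holds in a limited form. The intervention is delivered in groups and household members share an arm, yet the sample size and the primary model assume independence and no planned analysis checks that assumption. The 80% power and 5% error are not assured; the SAP does not show that they are wrong.

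With an assumed 6 to 10 analysed per group, the effect is negligible at ICC 0.01 and material from about ICC 0.05. The power figures assume 202 evaluable and no gain from baseline adjustment.

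It would also be too strong to describe the controls as fully independent, since the household rule applies to them too.

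**What to change.** - **Section 4.5.1.** Keep the same mean model. Use either cluster-robust standard errors with a small-sample correction or a partially nested mixed model. Define clusters by assigned education group in the intervention arm, and by household (or individual, if alone) in the control arm. At minimum, pre-specify this under 4.5.2 as a sensitivity analysis of the primary outcome.
- **Cluster membership.** Take the assigned group from the session booking where available, so that non-attenders keep their allocation. If membership changed between sessions, say how that is handled.
- **Reporting.** Report the estimated ICC.
- **Section 1.2.6.** The planning calculation can stay as the record of the design. Add a note beside it that the 80% power assumes no clustering, with a range over plausible ICCs and the assumed group size.

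The cost is SAP wording, some analysis code and retrieval of the booking records. The interval may be slightly wider and the stated power less favourable. If the ICC is near zero, the result will be almost the one already planned.
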